8. RESEARCH QUESTION AND OBJECTIVES

The research question is to assess the one-year and two-year benefit-risk of rivaroxaban for SPAF compared to VKA and dabigatran among new anticoagulant users.

The main study objective is to compare the one-year and two-year risk of each of the following individual outcomes: Stroke and systemic embolism (SE), major bleeding and death between new users of anticoagulant for SPAF during drug exposure: rivaroxaban versus VKA, and rivaroxaban versus dabigatran.

Secondary objectives are:

- To describe the drug exposure to rivaroxaban, dabigatran, and VKA for SPAF in new users, as well as pattern of use;

¹ Agence Nationale de Sécurité du Médicament et des produits de santé (French Medicines Agency)

² Caisse Nationale de l'Assurance Maladie des Travailleurs Salariés (French National Health Insurance Fund for Salaried Workers)

- To compare the one-year and two-year risk of the following individual outcomes: a composite of stroke and SE, major bleeding and death, clinically relevant bleeding (CRB) and acute coronary syndrome (ACS) between new users of anticoagulant for SPAF during drug exposure: rivaroxaban versus VKA, and rivaroxaban versus dabigatran;
- To estimate the cumulative incidence and the incidence rate of each individual main and secondary outcome (stroke and SE, major bleeding, CRB, death, composite criteria, and ACS), as well as according individual diagnose of each of these outcomes, during drug exposure for rivaroxaban, dabigatran, and VKA;
- To estimate the cumulative incidence of each individual main and secondary outcome (stroke and SE, major bleeding, CRB, death, composite criteria, and ACS), as well as according individual diagnose of each of these outcomes during post-anticoagulant exposure for rivaroxaban, dabigatran, and VKA (i.e. after anticoagulant discontinuation);
- To assess outcome risk factors, including (but not limited to), gender, age, stroke and bleeding risk scores (CHA₂DS₂-VASc and HAS-BLED), low or high dosage at index date for DOAC, drug predisposing to bleeding during drug exposure and significant baseline characteristics;
- To describe and compare healthcare resources utilisation related to SPAF during rivaroxaban, dabigatran, and VKA exposure, including outcomes, and their related costs from the societal perspective and from the French healthcare insurance perspective.

9. RESEARCH METHODS

9.1. STUDY DESIGN

The design is a cohort study in a healthcare claims and hospitalisation database including new users of rivaroxaban, dabigatran, or VKA for SPAF with a follow-up for at least one year and up to two years per subject. The overall design of the study is presented in the following figure (Figure 1).

Data will be extracted from 1 January 2010 to 31 December 2015. The index date will be the first reimbursed dispensation of rivaroxaban, dabigatran, or VKA in 2013 or 2014, without dispensation of any of them within the 3 years before index date. The study follow-up period will start on the study index date and will end two years later, or until the date of death with a right censoring on 31 December 2015 (at least a one year follow-up period except for death). Rivaroxaban, dabigatran, and VKA exposure will be defined during the study follow-up period, as well as the occurrence of each of the study outcome.

The main advantages of this study are that data are collected independently of the research question, allowing the conduct of a nationwide population-based historical cohort. Limits of database analyses are discussed later (Section 9.9 Limitations of the research methods).

[figure not shown]

Figure 1: Study design

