9.3.3. Exposure

Exposure definitions will use the following variables:

- **VKA** will be defined as B01AA ATC code;
- **DOAC** will be defined as B01AF01 ATC code for rivaroxaban and B01AE07 ATC code for dabigatran;
- **DOAC high dosage** will be defined using CIP codes for rivaroxaban 20mg and dabigatran 150mg;
- **DOAC low dosage** will be defined using CIP codes for rivaroxaban 15mg and dabigatran 110mg;
- **Treatment group** will be defined by the first anticoagulant dispensation during the inclusion period, i.e. rivaroxaban high or low dosage, dabigatran high or low dosage, or VKA;
- **Index date** will be defined as the date of the first dispensation of the anticoagulant in the treatment group;
- **Duration of a drug dispensation** will be defined as the number of daily doses for DOAC and 30 days for VKA;
- **Drug (DOAC or VKA) exposure** will be defined as the period starting at the index date and ending at the date of the last drug dispensation plus the duration of the last drug dispensation for subject with a drug discontinuation (defined below) or at the date of drug switch (defined below), or at the end of follow-up, whichever is the earliest;
- **Drug (DOAC or VKA) discontinuation** will be defined with a grace period of 60 days for the main analysis and 30 days for a sensitive analysis after the last dispensation plus the duration of the last drug dispensation;
- **Drug (DOAC or VKA) switch** defined as a dispensation of another anticoagulant, including heparin and LMWH dispensation (B01AB ATC code), for subject with a drug discontinuation;
- **Post drug (DOAC or VKA) exposure** will be defined as the period starting at date of the end of drug exposure (see above) and ending at the date a new prescription of an anticoagulant or at the end of follow-up, whichever is the earliest;
- **DOAC compliance** will be estimated using Medication Possession Ratio (MPR) during drug exposure defined by the number of defined daily doses dispensed, divided by the number of days of drug exposure for DOAC. Considering the variable dosage of VKA between subjects and over time in individual subjects, no defined daily dose can be defined, and therefore no MPR for VKA exposure.
- During a hospitalisation, drugs are provided by the hospital, and this time will be taken into account for calculation of drug exposure and drug discontinuation.

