Non-hospital data are updated every month and hospital-discharge summaries yearly at end of Q3 for the previous year. Access to SNIIRAM is regulated and needs approval from Institute of Health Data (*Institut des Données de Santé - IDS*) and French data protection commission (*Commission Nationale de l'Informatique et des Libertés - CNIL*).

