9.7.6. Drug exposure

Description of drug use patterns including drug MPR for DOAC, dosage, treatment discontinuation, switch to another anticoagulant, co-dispensation of drug predisposing to bleeding, and one-year and two-year treatment maintenance for all and matched subjects according to the treatment group, with standardised difference for each comparison planned (rivaroxaban versus VKA, and rivaroxaban versus dabigatran).

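### A supply that runs out within one grace period of 31 December 2015 cannot be confirmed as a discontinuation, so treatment maintenance is biased slightly upward by an amount that depends on an estimator the protocol does not name

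*Protocol*

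**What the plan says.** Section 9.1 of the protocol sets the calendar. "The index date will be the first reimbursed dispensation of rivaroxaban, dabigatran, or VKA in 2013 or 2014", and follow-up "will end two years later, or until the date of death with a right censoring on 31 December 2015". The data window is "Data will be extracted from 1 January 2010 to 31 December 2015". The extract and the administrative censoring date therefore coincide. Section 9.1 also says that "VKA exposure will be defined during the study follow-up period" (the sentence covers all three drugs), without saying whether dispensations after a subject's own two-year end may be consulted.

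Under section 9.3.3, exposure ends at the end of the last supply if there is a discontinuation, at a switch, or otherwise at the end of follow-up. Discontinuation "will be defined with a grace period of 60 days for the main analysis and 30 days for a sensitive analysis". Section 9.7.1 Generalities reverses this, with 30 days for the main analysis and 60 for sensitivity. The abstract contains both versions.

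Section 9.7.6 plans to describe "one-year and two-year treatment maintenance for all and matched subjects" by treatment group, with standardised differences for the two comparisons. It names no estimator. The limitations in section 9.9 discuss the grace period but not the end of the data.

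**The concern.** A stop is recognised only by looking forward one grace period past the end of supply. In the last 30 or 60 days of the extract there is nothing to look forward into. A patient who runs out on 20 November 2015 and never refills is, with a 60-day grace, carried as on drug to 31 December. The same gap a year earlier would end exposure at the end of supply. The written rules thus treat identical gaps differently by calendar date, and always in the direction of longer persistence.

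At stake is the first secondary objective, the description of drug exposure, and in particular second-year maintenance by arm. An arm with more stops gains somewhat more over the rates examined here, so a difference in persistence is slightly compressed.

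**Working it through.** **The plan's own figure.** Section 9.9 gives 90 days from last dispensation to a declared withdrawal: 30 days' supply + 60 days' grace = 90. Reproduced.

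**Calendar.** The last confirmable run-out is 31 December 2015 minus the grace period: 1 December (30 days) or 1 November (60 days).
- 2014 entrants: all are cut on 31 December 2015, and none completes a full two years.
- 2013 entrants: each ends on the two-year anniversary. That date falls in the unconfirmable window for 30/365 = 8.2% or 60/365 = 16.4% of the entry year. The others have more data in the extract, up to 364 days for a 1 January 2013 index date.

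**Inputs.** Entry is assumed uniform over 2013-2014. The protocol gives no stop rate, so a constant h of 0.15, 0.30 or 0.50 per year is assumed. Deaths and switches are left out. G is the grace period in years (0.0822 or 0.1644), and true two-year maintenance is S = exp(-2h).

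**Formulas, worked for h = 0.30 and a 60-day grace (S = 54.9%).**

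1. Crude proportion in 2013 entrants, whole extract used. Excess is about G × S × hG/2 = 0.1644 × 0.549 × 0.0247 = 0.0022, or 0.2 points.
2. Kaplan-Meier pooling both entry years, whole extract used. At u years since index (second year), a share G/(3-u) of those at risk is in the window. Missed cumulative hazard is hG ln 2 + hG²/4 = 0.0342 + 0.0020 = 0.0362. The estimate is 54.9 × exp(0.0362) = 56.9%. Simulation gives 57.0%, slightly more because missed stoppers also stay in the risk set.
3. Crude proportion, only dispensations within each subject's own follow-up used. Excess is exp(-h(2-G)) - exp(-2h) = 0.577 - 0.549 = 2.8 points.
4. Kaplan-Meier on the same restriction. No stop is confirmable in the last G of year two, so missed cumulative hazard is h[G ln(2/(1+G)) + G + G²/4] = 0.30 × 0.260 = 0.0780. The estimate is 54.9 × exp(0.0780) = 59.3%. Simulation gives 59.4%.

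**Simulation, 2 million entrants per row; overstatement of two-year maintenance in points.**

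| Stop rate per year | Grace | True % | Crude 2013, whole extract | Pooled KM, whole extract | Crude 2013, own follow-up only | Pooled KM, own follow-up only |
|---|---|---|---|---|---|---|
| 0.15 | 30 d | 74.1 | 0.04 | 0.7 | 0.9 | 1.5 |
| 0.15 | 60 d | 74.1 | 0.15 | 1.4 | 1.8 | 2.9 |
| 0.30 | 30 d | 54.9 | 0.06 | 1.0 | 1.4 | 2.3 |
| 0.30 | 60 d | 54.9 | 0.22 | 2.1 | 2.8 | 4.5 |
| 0.50 | 30 d | 36.8 | 0.07 | 1.1 | 1.5 | 2.6 |
| 0.50 | 60 d | 36.8 | 0.26 | 2.4 | 3.2 | 5.2 |

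One-year Kaplan-Meier maintenance moves by at most 0.2 points. Misassigned exposed time is 0.01% to 0.26% of the total. Censoring persistence one grace period before 31 December 2015, with later dispensations in the extract used to confirm stops, brings the pooled Kaplan-Meier error to 0.02 points or less in every row.

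**The case against.** Several stronger readings are tempting, and the protocol does not support them.

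- A reader might infer that follow-up stops on 31 December 2015 for everyone. It does not: 2013 entrants, the only ones who can complete two years, stop at their anniversary, and most have enough later data to confirm a stop.
- A reader might take the pooled Kaplan-Meier figure as the size of the error. The protocol names Kaplan-Meier only for death, and section 9.7.2 Healthcare resources and cost restricts its two-year description to 2013 entrants. If maintenance were handled likewise and the whole extract used, the error would be at most about 0.3 points.
- A reader might infer that no stop at all is detected in the window. A switch still shows as a dispensation of another anticoagulant; only stops without one are lost.
- A reader might infer bias in the stroke, bleeding or death comparisons. With at most about 0.3% of exposed time misassigned, the hazard ratios barely move.
- Compression between arms is small. For rates of 0.15 against 0.50 and a 60-day grace (pooled Kaplan-Meier, whole extract), the true gap is 74.1 - 36.8 = 37.3 points and the biased gap is 75.5 - 39.2 = 36.3.

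It can also be said that section 9.6 leaves decision rules and exposure definitions to the statistical analysis plan. That is fair as regards the remedy. But this is more than missing detail: the protocol itself fixes the data window and the rule that unconfirmed stops count as exposure, and following both as written produces the bias.

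**Conclusion.** The point holds as a minor one. The end of the extract, the censoring date and the grace-period rule together make stops without a switch unconfirmable in the last 30 or 60 days of data, and the resulting bias in maintenance is upward in every scenario examined. Its size is not fixed by the protocol. It depends on the estimator, on whether dispensations after a subject's own two-year end are used, on which grace period applies, and on stop rates that are assumed here. Over those choices the two-year overstatement runs from about 0.04 to about 5 points. It concerns a descriptive secondary result and leaves the main objective essentially untouched.

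**What to change.** 1. Censor the maintenance and discontinuation estimates one grace period before 31 December 2015, leaving outcome follow-up as it is. The cost is the last 30 to 60 days of persistence time; late-2014 entrants then contribute slightly less than one year to these estimates.
2. State that dispensations after a subject's own two-year end but within the extract are used to confirm stops. This costs nothing and removes the largest version of the error.
3. Name the estimator for one- and two-year maintenance and the entry years it includes.
4. Reconcile the main-analysis grace period between section 9.3.3, section 9.7.1 Generalities and the abstract, since it sets the length of the window.

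Optionally, also extract outpatient anticoagulant dispensations to at least 29 February 2016 (31 December 2015 plus 60 days), solely to confirm stops. Section 9.4 says "Non-hospital data are updated every month" and extraction is planned for Q3-Q4 2016, so these claims should exist; the data request would have to cover them. This is not a complete substitute. Section 9.3.3 requires hospital time to be taken into account, and hospital summaries arrive only at the end of Q3 for the previous year. Stays in 2016 would be missing both at extraction and at the Q2 2017 final report, so some gaps caused by a hospital stay could be misread as stops.

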9.2. SETTING

This is a study of subjects with a first dispensation of an anticoagulant (VKA or DOAC) for SPAF in a real world setting, identified and followed in the French national claims and hospital database (SNIIRAM).

Population definition

All subjects with a first reimbursed dispensation of rivaroxaban (15 or 20 mg), dabigatran (110 or 150 mg) or VKA in 2013 or 2014 will be extracted from the database. Among them, some will have clear AF diagnosis information, some an indication other than AF and other no clear information about anticoagulant indication. To overcome this obstacle, we will use two diagnosis definitions for AF, a specific definition in order to minimize the risk of false positives, and a sensitive definition in order to minimize the risk of false negatives, in such a way that two NVAF cohorts will be defined:

- **Specific NVAF cohort** (for the main analysis) will include definite NVAF subjects as defined below;
- **Sensitive NVAF cohort** (as secondary analysis) will include definite NVAF and probable NVAF subjects as defined below.

Definite NVAF subjects will be defined with all the following inclusion criteria:

- A first reimbursed dispensation of rivaroxaban, dabigatran, or VKA in 2013 or 2014, and
- No previous DOAC (rivaroxaban, dabigatran, apixaban) or VKA dispensation during the previous three years,
- Definite AF information in the database (see variable definition below),
- No other indication for the use of anticoagulant (treatment of venous thromboembolic events (VTE), prevention of VTE after orthopaedic surgery),
- No history of rheumatic valve disease or valve replacement (non-valvular AF definition from the 2012 European Society of cardiology guidelines, Camm 2012).

Probable NVAF subjects will be defined with all the following inclusion criteria:

- A first reimbursed dispensation of rivaroxaban, dabigatran, or VKA in 2013 or 2014, and
- No previous DOAC (rivaroxaban, dabigatran, apixaban) or VKA dispensation during the previous three years,
- Probable AF information in the database (using the development of an AF disease score, see variables definition below),
- No other indication for the use of anticoagulant (treatment of VTE, prevention of VTE after orthopaedic surgery),
- No history of rheumatic valve disease or valve replacement (non-valvular AF definition from the 2012 European Society of cardiology guidelines, Camm 2012).

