In France, Xarelto[®] and Pradaxa[®] were launched in this indication in August 2012, and Eliquis[®] in January 2014. The Transparency Committee of the *Haute Autorité de Santé* (HAS) gave a positive opinion for the reimbursement in this indication with a substantial medical benefit (SMR important) but no improvement in existing benefit (ASMR V), no expected public health impact, and a target population of 500 000 patients. As part of this procedure, the Transparency Committee requested Bayer to provide additional data documenting the therapeutic benefit of Xarelto[®] under actual conditions of use compared with the normal treatment of at-risk patients with NVAf:

- The characteristics of the treated patients, in particular age, gender, history and cardiovascular risk factors,
- The conditions of use of Xarelto[®]: reasons for starting treatment (particularly, first-line or second-line prescription, and risk factors associated with AF), any previous anticoagulant treatment and level of control thus obtained, concomitant treatments (in particular, antiplatelet agents and medicines with a risk of interaction), prescribed dosage (dose, amount administered daily and duration of prescription), frequency and reasons for any discontinuation of treatment and treatments started as a back-up,
- The impact on morbidity and mortality (events avoided and adverse effects, particularly bleeding), treatment compliance and quality of life in the medium and long term.

ANSM,¹ the French medicines agency, commissioned two studies using the French national claims and hospital database:

- The NACORA-BR study, performed by the CNAMTS,² was a cohort study with a main objective to compare the short-term risk of major bleeding for new NOAC users naive of VKA during the second half of 2012 to new users of VKA during the second half of 2011. Secondary objectives were to compare the risk of arterial events (stroke, systemic embolism), the risk of myocardial infarction (MI) over the same period in patients starting treatment within the AF indication, and the 30-day survival for patients hospitalized for major bleeding. This study concluded to no significant statistical difference between NOACs, dabigatran or rivaroxaban, and VKAs for the short-term risk of bleeding or arterial thromboembolic short-term risk during the early phase of anticoagulant therapy in NVAF patients (CNAMTS 2014, Maura 2015).

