9.4. DATA SOURCES

The SNIIRAM database is the national healthcare insurance system database linked to the national hospital-discharge summary database (*Programme de Médicalisation des Systèmes d'Information*, PMSI) and the national death registry, using a unique pseudonymized identifier. It includes the three main healthcare insurance funds (CNAMTS³, MSA⁴, RSI⁵), which represent about 96% of the French population, and currently some of the 19 other smaller French healthcare insurances for specific professional organisations such as militaries, deputies and senators, priests, Opera... (Moulis 2015). To the extent that the SNIIRAM is a national database, all subjects are followed-up until they died. The only dropouts are subjects who leave the country to live abroad and those who join one of the smaller French healthcare insurance organisations not yet included in the SNIIRAM, which is rare and not linked with a disease or healthcare package. The SNIIRAM contains individual pseudonymised information on (Tuppin 2010, Moulis 2015):

- General characteristics: gender, year of birth, affiliation scheme, area of residence;
- Month and year of death;
- Long-term disease (LTD, or ALD in French, and associated ICD-10 codes) with starting and ending date. There is a list of 30 LTD for a total of 3448 available ICD-10 codes, which includes most of chronic diseases with long term and/or expensive treatment; e.g. a disease such as AF is specified by the ICD-10 code within LTD. Registration with a LTD is obtained at the request of a patient's general practitioner and must be validated by the health insurance system physician. Once registered, patients receive full (i.e. 100%) reimbursement for expenditure related to the LTD, as defined by the health authorities. The LTD information is specific for the diagnosis (very low risk of false positives), but not sensitive because not all patients with the disease ask to benefit from a LTD;
- Outpatient reimbursed healthcare expenditures: visits, medical procedures, medical imageries, lab tests, drugs, medical devices, transports, sick leaves... with prescriber and professional caregiver information (medical or paramedical specialty, private/public practice), dates (prescription and dispensation), and codes (but not the medical indication nor result);

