9.9. LIMITATIONS OF THE RESEARCH METHODS

The SNIIRAM is a national healthcare claims database linked to the national hospital discharge summaries database that covers more than 95% of the French population. It provides a unique opportunity to identify all new users of DOAC or VKA in NVAF in 2013-2014, with exhaustive information about reimbursed treatments out of hospital and use of reimbursed healthcare resources, as well as all hospitalisations for the outcomes of interest. Furthermore, the SNIIRAM has the advantage of any study extracting patient records from an existing database that are not impacted by the study.

This is also the main limit of this claims and hospitalisation database that was built for administrative and reimbursement purposes with a lack of clinical data and biological results, including some risk factors such as smoking status, body mass index, blood pressure, and cholesterol values, that could be impact the patient prognosis. However, statistical methods such as PS and hdPS were developed to improve control of confounding using a large number of covariates ascertained from patients' healthcare claims data, as these variables may collectively be proxies for unmeasured confounders (Schneeweiss 2009, Rassen 2012).

Selection bias

Since all subjects identified with extraction criteria in 2013-2014 will be extracted from a national database, there is no study selection bias, nor attrition bias, except very rare withdrawals from one of the healthcare insurance systems including and covering more than 95% of the French population.

Information bias

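### New-user status rests on no dispensation being seen in three years, but no criterion requires that each subject was covered by the database for those three years

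*Protocol*

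**What the plan says.** Protocol section 9.2 lists the criteria for definite and probable NVAF subjects and says that all must be met. Two of them define new use: "A first reimbursed dispensation of rivaroxaban, dabigatran, or VKA in 2013 or 2014, and" (the list continues) and "No previous DOAC (rivaroxaban, dabigatran, apixaban) or VKA dispensation during the previous three years". Section 9.1 repeats the rule for the index date: "without dispensation of any of them within the 3 years before index date". The data window is fixed there too: "Data will be extracted from 1 January 2010 to 31 December 2015".

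On coverage, section 9.4 names three main funds, "which represent about 96% of the French population", and says that only some of 19 smaller schemes are currently included. Among the few people lost to the database it counts "those who join one of the smaller French healthcare insurance organisations not yet included in the SNIIRAM". It does not mention people whose records begin part-way.

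Section 9.9 concludes that "there is no study selection bias, nor attrition bias, except very rare withdrawals from one of the healthcare insurance systems".

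**The concern.** A look-back without a dispensation shows new use only if a dispensation would have been seen. For someone who came under a covered scheme or arrived in France shortly before index, or whose scheme was added then, the criterion is met by default.

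Two things are at stake.

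- **Who is in the cohort.** Some continuing users would be taken as starters. They have already come through the early treatment period, so their event rate may differ from that of true starters. If they fall mainly in the VKA arm, the rivaroxaban-VKA comparison is shifted.
- **What is known about them.** The same three-year window serves the rheumatic-valve and valve-replacement exclusions (9.3.2), CHA2DS2-VASc and HAS-BLED (9.3.5), and the drug and healthcare counts in the hdPS (9.3.5, 9.7.3). A short record can leave an exclusion untriggered and a score too low. Matching on the hdPS (9.7.4) cannot repair covariates that were truncated before the score was built.

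This is not a detail left to the statistical analysis plan: section 9.2 fixes eligibility, and section 9.9 draws a conclusion from it.

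**Working it through.** **1. Calendar look-back.** From 1 January 2010 to the earliest index date, 1 January 2013, is 365 + 365 + 366 = 1 096 days, or three years. For the last index date, 31 December 2014, it is 1 825 days. The stated three years are reproduced, so the extraction window is long enough. The gap is in individual coverage only.

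**2. Who can be misclassified.** Section 9.3.3 counts 30 days per VKA dispensation, so a continuing user is seen often.

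- Continuing user, records start in 2010-2012: normally shows a dispensation before 2013 and is excluded by the criterion.
- Continuing user, first visible dispensation in 2013-2014: admitted as new.
- Person who stopped before entry and restarted in 2013-2014: admitted as new if no dispensation is seen in the look-back.
- Genuine starter with a short record: correctly new, but with incomplete three-year history, in any arm.

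**3. Which arm.** Rivaroxaban and dabigatran were launched for this indication in August 2012 (section 7), about 5 months before the first index date and about 29 months before the last. Unseen continuing users are therefore probably mostly on VKA early in the index period, and less so later. If DOACs held an assumed 5% to 40% of the treated stock, 95% to 60% of misclassified continuing users would be on VKA. An unseen VKA user who switches would enter a DOAC arm.

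**4. How many (illustration only).** The protocol gives neither an entry rate nor a count of treated patients. Assume a yearly entry rate e of 0.05% to 1% and a treated stock P of 250 000 to 500 000. The upper value borrows "a target population of 500 000 patients" from section 7 as a ceiling. Over the two index years, misclassified = 2 × e × P:

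| e per year | P = 250 000 | P = 500 000 |
|---|---|---|
| 0.05% | 250 | 500 |
| 0.1% | 500 | 1 000 |
| 0.5% | 2 500 | 5 000 |
| 1% | 5 000 | 10 000 |

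Added to the 100 000 expected in the specific cohort (section 9.5), the share runs from 250 / 100 250 = 0.25% to 10 000 / 110 000 = 9.1%. No reduction is made for the AF-record requirement, so these are upper values for each pair of assumptions.

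**5. Effect on the hazard ratio.** Let c be the misclassified share of the VKA arm and r the assumed ratio of their event rate to that of true starters. The rivaroxaban-VKA hazard ratio is then multiplied by 1 / (1 − c(1 − r)).

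- c = 0.5%, r = 0.8: 1 / (1 − 0.005 × 0.2) = 1.001
- c = 2%, r = 0.5: 1 / (1 − 0.02 × 0.5) = 1.010
- c = 9%, r = 0.5: 1 / (1 − 0.09 × 0.5) = 1.047

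Here c is a share of one arm, not of the cohort. In the most extreme corner, all 10 000 would join an assumed VKA arm of 50 000. Then c = 10 000 / 60 000 = 16.7%, and with r = 0.5 the factor is 1 / (1 − 0.167 × 0.5) = 1.09. That needs every assumption at its worst and no loss to the AF filter.

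**The case against.** The best defence is that the database is national. The three main funds cover about 96% of the population, so schemes still being added concern at most part of the remaining 100 − 96 = 4%. The protocol does not say that any scheme joined in 2013-2014. Records are linked by a unique identifier, and nothing suggests that a move between covered funds erases history. The main analysis also needs a hospital record, procedure or long-term-disease registration for AF within 36 months before or six months after index (9.3.1), and a stable long-term user with a fresh record has little pre-index time to show one.

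Most of this stands and is why the effect is probably small. It does not close the gap. Entry is never discussed, the AF record may fall after index, and the AF requirement does nothing for truncated covariates in those it admits.

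A reader might also infer stronger claims, which the protocol does not support:

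- **Everyone whose records start inside the look-back is falsely new.** Continuing users first recorded in 2010-2012 would normally be excluded.
- **Nearly all misclassified users are in the VKA arm, so the bias is one-sided.** No figure shows this. DOACs had been available for about 29 months by the last index date, and section 7 itself describes a study of patients switching from VKA to DOAC.
- **All look-back covariates are blank.** Age and sex still enter the scores and the hdPS, and long-term-disease registrations carry their own start dates.
- **There were 500 000 treated patients.** The figure is a target population from a reimbursement opinion, not a count of VKA users.

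**Conclusion.** The point holds in a limited form. Section 9.2 sets no individual coverage requirement for the period on which new-user status and much of the covariate history depend, and section 9.9 rules out selection bias after considering exits only. As written, the rule admits some unseen continuing or restarting users and leaves short records incomplete in any arm.

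The number affected cannot be computed from the protocol. The range of 250 to 10 000 subjects and the hazard-ratio factor of about 1.001 to 1.047 rest on assumed values for the entry rate, the treated stock, the misclassified share of the VKA arm and the event-rate ratio. The direction of the shift also depends on continuing users having the lower event rate and being mainly on VKA. Within those limits the effect is probably small, but it should be measured and not taken as zero.

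**What to change.** - In section 9.2, for both the specific and the sensitive cohort, require affiliation for at least the 36 months before index to a scheme whose data were in the SNIIRAM throughout. Data from 1 January 2010 make this checkable for every index date. Section 9.4 lists affiliation scheme among the available variables; the data extraction plan (9.6) should make sure that its history, and the date each scheme joined, are obtained.
- In the flow chart (9.7.5), report the number excluded by this criterion for rivaroxaban, dabigatran and VKA separately.
- Run a stricter rule, at least one claim of any kind in each of the three years before index, as a sensitivity analysis only. It also removes genuine low users of care, possibly unequally by drug.
- Reword the selection-bias statement in section 9.9 to acknowledge late entry as well as withdrawal.

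The cost is one added filter and a probably small loss of subjects.
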